9.3 Schedule of Activities

The Schedule of Activities (see [Appendix A: Schedule of Activities](#)) shows the timing of planned study procedures. Every effort should be made to adhere to this procedure schedule and all assessments should be completed at each study visit. Where possible, study visits should be performed and scheduled as part of a patients regularly scheduled dialysis session.

9.3.1 Prescreening Visit

To minimize screen failures, there will be an optional Prescreening visit which will enable the subject to have a HemoCue Hb prior to proceeding with full Screening. Subjects will need to sign an abbreviated Prescreening informed consent form or full consent form prior to Prescreening. If the Prescreen HemoCue Hb is between 8.0 and 11.0 g/dL (inclusive), the investigative site may proceed with SV1, which preferably will occur on the same day as Prescreening.

9.3.2 Screening Visits

Subjects will need to sign a full consent form prior to SV1 procedures. The consent form may be signed in advance of SV1 procedures. The Screening period starts at the time the informed consent is signed and will be a maximum of 8 weeks in duration. Two Screening visits (SV1 and SV2) must be performed within 8 weeks prior to dosing (Baseline visit/Day 1). There must be a minimum of 4 days between the 2 Screening visits and a minimum of 4 days between SV2 or last retest and the Baseline visit.

The Investigator will maintain a log of subjects (both Prescreened and Screened) and indicate who of the prescreened subjects were brought in for informed consent and Screening and who of the Screened subjects were enrolled or excluded and the reason for exclusion.

After obtaining informed consent, subjects will undergo a number of screening activities.

9.3.2.1 Screening Visit 1 (SV1)

At SV1, the following activities/procedures will be performed:

- Informed consent (including an additional optional consent for blood samples for future genetic analyses).
- Review of eligibility criteria.
- Vital signs including heart rate and blood pressure (assessed in seated position after 5 minutes of rest and prior to blood draws).
- Laboratory procedures:
 - CBC (without differential).
 - Iron indices.
 - Folate and vitamin B₁₂ levels.
 - Serum chemistry.
 - Liver function tests.
- Visit registration in IWR.

Refer to [Section 7.4.1, Retesting](#) and [Section 7.4.2, Rescreening](#) for further details regarding repeating laboratory measurements during the Screening period.

9.3.2.2 Screening Visit 2 (SV2)

At SV2, the following activities/procedures will be performed:

- Review of eligibility criteria.
- Physical examination.
- Demographics and medical history.
- Vital signs including heart rate and blood pressure (assessed in seated position after 5 minutes of rest and prior to blood draws), as well as height and dry weight.
- Laboratory procedures:
 - CBC (without differential).
 - Serum pregnancy test for females of childbearing potential (eligible subjects will be advised to use an adequate contraceptive method).
- Prior and current medication use.

The mean of 2 Hb values from the central laboratory must be between 8.0 and 11.0 g/dL (inclusive) to qualify for inclusion into the trial. If the subject's Hb does not qualify after SV1, SV2 or retest Hb, the subject should be considered a screen failure.

9.3.2.3 Subject Retesting

Subjects who initially fail to qualify for the study based on laboratory test results may be retested once within the 8-week Screening period, per Investigator discretion (Section 7.4.1, Retesting).

9.3.3 Subject Rescreening

Subjects who fail to meet the qualifying criteria for Hb during the Screening period may be considered for rescreening at the discretion of the Investigator if it is felt that the subject's status has progressed and that the subject may now qualify for the study. Additionally, subjects who fail to qualify for the study based on low TSAT, ferritin, folate, or B₁₂ values may be considered for rescreening after receiving replacement therapy. Screening is limited to 3 attempts (initial

Screening and 2 additional rescreening attempts) ([Section 7.4.2, Rescreening](#)) and the Inclusion Criteria for initiating chronic maintenance dialysis within 16 weeks prior to Screening must continue to be met based on the date of the Rescreening visit.

9.3.4 Baseline Visit (Day 1)

The Baseline visit must be performed at a minimum of 4 days from the last Screening visit (SV2) procedure, including retest(s).

At the Baseline visit, the following activities/procedures will be performed:

- Randomization.
- 12-lead ECG (prior to vital sign assessments and blood draws).
- Vital signs including heart rate and blood pressure (assessed in seated position after 5 minutes of rest and prior to blood draws).
- Laboratory Procedures:
 - Coagulation Tests.
 - CRP.
 - CBC (including differential).
 - Reticulocyte count.
 - Serum chemistry.
 - Liver function tests.
 - Iron indices.
 - Lipid profile.
 - EPO.
 - Biomarkers.
 - PK (see [Section 9.2.2, Laboratory Evaluations](#); samples will be drawn only for subjects randomly assigned to vadadustat).
 - Exploratory samples.
- Review of medical history for new conditions since Screening visit.
- Medication use since Screening visit.
- Study medication assessments and procedures:
 - Subject will take their first dose of study medication at the investigative site during the Baseline visit.
 - Hb by HemoCue.
 - Assess:
 - Hemodialysis vascular access type use changes.
 - Renal replacement therapy changes.
 - Dialysis adequacy, as available from local collection.
 - Vadadustat dispensing.
 - Darbepoetin alfa dispensing.
 - Iron supplementation as needed to maintain ferritin \geq 100 ng/mL or TSAT \geq 20% (per local product label; see [Section 8.4.6, Iron Supplementation](#)).
 - Visit registration in IWR.

- Safety assessments:
 - AE assessment as needed (after receiving the first dose of study medication).

9.3.5 Year 1 Treatment Period Visits (Day 2 through Week 52)

During the Year 1 Treatment Period visits at Weeks 2, 4, 6, 8, 10, 12, 16, 20, 24, 28, 32, 36, 40, 44, 48, and 52, the following activities/procedures will be performed:

- Vital signs including heart rate and blood pressure (assessed in seated position after 5 minutes of rest and prior to blood draws).
- Dry weight (Weeks 12, 24, 36, and 52).
- Laboratory procedures:
 - CBC (Weeks 2, 4, 6, 8, 10, 12, 16, 20, 24, 28, 32, 36, 40, 44, 48, and 52; differential at Weeks 28 and 52).
 - Reticulocyte count (Weeks 4, 12, 28, and 52).
 - Serum chemistry (Weeks 28 and 52).
 - Liver function tests (Weeks 4, 8, 12, 16, 20, 24, 28, 36, 44, and 52).
 - Iron indices (Weeks 4, 8, 12, 20, 28, 36, 44, and 52).
 - Lipid profile (Weeks 28 and 52).
 - EPO (Weeks 4, 12, 28, and 52).
 - CRP (Weeks 28 and 52).
 - Biomarkers (Weeks 12, 28, and 52).
 - PK (Weeks 4, 12, 28, and 52; see [Section 9.2.2, Laboratory Evaluations](#); samples to be drawn only for subjects randomized to vadadustat).
 - Exploratory samples (Weeks 28 and 52).
- Record date and time of subject's last dose of vadadustat prior to the PK sample (Weeks 4, 12, 28, and 52).
- Safety assessments:
 - AE assessment.
 - RBC transfusions and ESA rescue
 - Therapeutic phlebotomy
 - MACE endpoint questionnaire.
- Medication assessments and procedures:
 - Review of concomitant medications.
 - Hb by HemoCue for dose adjustment.
 - Assess:
 - Hemodialysis vascular access type use changes.
 - Renal replacement therapy changes.
 - Dialysis adequacy, as available from local collection.
 - Drug reconciliation: Study medication (vadadustat or darbepoetin alfa) reconciliation will be conducted per the pharmacy manual instructions.
 - Visit registration in IWR.
 - Vadadustat dispensing as needed per [Section 8.2.1, Dispensing of Vadadustat](#).
 - Darbepoetin alfa dispensing.
 - Iron supplementation as needed to maintain ferritin \geq 100 ng/mL or TSAT \geq 20% (per local product label; see [Section 8.4.6, Iron Supplementation](#)).

- Question subject regarding dosing compliance and whether they have questions or have experienced any problems related to the dosing of study medication (vadadustat or darbepoetin alfa).

9.3.6 Year 2-4 Monthly Hb Monitoring

Monthly monitoring of Hb as part of local standard of care labs or at unscheduled visits for dose adjustment.

9.3.7 Year 2 Treatment Period Visits (Weeks 53 through 104)

During the Year 2 Treatment Period visits at Weeks 64, 76, 88, and 104, the following activities/procedures will be performed:

- Vital signs including heart rate and blood pressure (assessed in seated position after 5 minutes of rest and prior to blood draws).
- Dry weight (Week 104).
- Laboratory Procedures:
 - CBC (Weeks 64, 76, 88, and 104; differential at Weeks 76 and 104).
 - Serum chemistry (Weeks 76 and 104).
 - Liver function tests (Weeks 64, 76, 88, and 104).
 - Iron indices (Weeks 64, 76, 88, and 104).
 - CRP (Week 104).
 - Biomarkers (Week 104).
 - Exploratory samples (Week 104).
- Safety assessments:
 - AE assessment.
 - RBC transfusions and ESA rescue.
 - Therapeutic phlebotomy.
 - MACE endpoint questionnaire.
- Medication assessments and procedures:
 - Review of concomitant medications.
 - Hb by HemoCue for dose adjustment.
 - Assess:
 - Hemodialysis vascular access type use changes.
 - Renal replacement therapy changes.
 - Dialysis adequacy, as available from local collection.
 - Drug reconciliation: Study medication (vadadustat or darbepoetin alfa) reconciliation will be conducted per the pharmacy manual instructions.
 - Visit registration in IWR.
 - Vadadustat dispensing as needed per [Section 8.2.1, Dispensing of Vadadustat](#).
 - Darbepoetin alfa dispensing.
 - Iron supplementation to maintain ferritin ≥ 100 ng/mL or TSAT $\geq 20\%$ (per local product label; see [Section 8.4.6, Iron Supplementation](#)).
 - Question subject regarding dosing compliance and whether they have questions or have experienced any problems related to the dosing of study medication (vadadustat or darbepoetin alfa).

9.3.8 Year 3/4 Treatment Period Visits (Weeks 116 through 208)

During the Year 3/4 Treatment Period visits at Weeks 116, 128, 140, 156, 168, 180, 192, and 208, the following activities/procedures will be performed:

- Vital signs including heart rate and blood pressure (assessed in seated position after 5 minutes of rest and prior to blood draws).
- Dry weight (Weeks 156 and 208).
- Laboratory Procedures:
 - CBC (Weeks 116, 128, 140, 156, 168, 180, 192, and 208; differential at Weeks 128, 156, 180, and 208).
 - Serum chemistry (Weeks 128, 156, 180, and 208).
 - Liver function tests (Weeks 116, 128, 140, 156, 168, 180, 192, and 208).
 - Iron indices (Weeks 116, 128, 140, 156, 168, 180, 192, and 208).
 - CRP (Week 156).
 - Biomarkers (Week 156).
 - Exploratory samples (Week 156).
- Safety Assessments
 - RBC transfusions and ESA rescue.
 - Therapeutic phlebotomy.
 - MACE endpoint questionnaire.
- Medication assessments and procedures:
 - Review of concomitant medications.
 - Hb by HemoCue for dose adjustment.
 - Assess:
 - Hemodialysis vascular access type use changes.
 - Renal replacement therapy changes.
 - Dialysis adequacy, as available from local collection.
 - Drug reconciliation: Study medication (vadadustat or darbepoetin alfa) reconciliation will be conducted per the pharmacy manual instructions.
 - Visit registration in IWR.
 - Vadadustat dispensing as needed per [Section 8.2.1, Dispensing of Vadadustat](#).
 - Darbepoetin alfa dispensing.
 - Iron supplementation to maintain ferritin ≥ 100 ng/mL or TSAT $\geq 20\%$ (per local product label; see [Section 8.4.6, Iron Supplementation](#)).
 - Question subject regarding dosing compliance and whether they have questions or have experienced any problems related to the dosing of study medication (vadadustat or darbepoetin alfa).

9.3.9 End of Treatment (EOT) Visit

The EOT visit will be performed at the time a subject permanently discontinues study medication or for subjects on study medication at the time of notification of global study completion. (See [Appendix A: Schedule of Activities](#)).

At the EOT visit, the following activities/procedures will be performed:

- Vital signs including heart rate and blood pressure (assessed in seated position after 5 minutes of rest and prior to blood draws), as well as dry weight.
- Laboratory Procedures:

- CBC (without differential).
- Serum chemistry.
- Liver function tests.
- Iron indices.
- Biomarkers.
- CRP.
- Exploratory samples.
- Safety assessments:
 - AE assessment.
 - RBC transfusions and ESA rescue.
 - Therapeutic phlebotomy.
 - MACE endpoint questionnaire.
- Recording of concomitant medications.
- Assess:
 - Hemodialysis vascular access type use changes.
 - Renal replacement therapy changes.
- Dialysis adequacy, as available from local collection.
- Drug reconciliation: Study medication (vadadustat or darbepoetin alfa) reconciliation will be conducted per the pharmacy manual instructions.
- Visit registration in IWR.
- Question subject regarding dosing compliance and whether they have experienced any problems related to the dosing of study medication (vadadustat or darbepoetin alfa).

9.3.10 Follow-up Visit

The Follow-up visit will be conducted in person or via the telephone 4 weeks after the EOT visit. The following activities/procedures will be performed:

- AE assessment.
- RBC transfusions and ESA rescue.
- Therapeutic phlebotomy.
- MACE endpoint questionnaire.
- Recording of concomitant medications.
- Dialysis adequacy, as available from local collection.

9.3.11 Unscheduled Visits

Unscheduled assessments may be conducted at any time as medically warranted. The following activities/procedures will be performed. At a minimum,

- MACE Endpoint Questionnaire
- AE assessments.
- Any other procedures that are medically warranted at the discretion of the Investigator.

9.3.12 End of Study Subject Status

The End of Study (EOS) assessment documents the subject status at the global study completion or at the time of subject withdrawal of consent or when subject is deemed LTFU or upon death. The table below outlines how to handle each subject based on their status.

The following activities/procedures will be performed. At minimum,

- EOS subject status

Subject Status	Global Study Completion
Subject on Study Medication (includes those on temporary interruption) at time of global study completion	
• Perform EOT visit• Perform the Follow-up visit 4 weeks after EOT and include EOS subject status
Subject permanently discontinued study medication and continues to be followed in the study	
Optimal data collection would include the following assessments:
 
• EOS subject status (must collect at minimum)• MACE Endpoint Questionnaire• AE Assessment 
NOTE: EOT and the Follow-up visit 4 weeks after EOT visit to be performed at time study medication is permanently discontinued.

Subject Lost to Follow-up	Work with third party vendor to ascertain vital status and complete EOS subject status. If subject-site contact is reestablished and possible, collect available information for EOS subject status.
Subject Withdrawn Consent	Complete the EOS subject status form at the time of withdrawal of consent, absolute refusal of ALL methods of MACE and health status follow-up.
Subject Death	Complete the EOS subject status form at the time of death (see Section 10 Adverse Events for more details on other actions related to reporting a death)

9.4 Study Medication Stopping Rules

Study medication must be permanently discontinued if a subject meets one of the criteria in Table 2 below

Table 2. Study Medication Stopping Rules

ALT or AST >3x ULN and total bilirubin >2x ULN	Permanently Discontinue Treatment
ALT or AST >3x ULN and INR >1.5	Permanently Discontinue Treatment
ALT or AST >8x ULN	Permanently Discontinue Treatment
ALT or AST remains >5x ULN over 2 weeks*	Permanently Discontinue Treatment

ALT or AST >3x ULN with symptoms including e.g., fatigue, nausea, vomiting, right upper quadrant pain, fever, rash or eosinophilia	Permanently Discontinue Treatment
--	-----------------------------------

* Re-challenge generally should be avoided with ALT or AST >5x ULN unless there are no other good therapeutic options.

ALT: alanine transferase; AST: asparagine transferase; INR: international normalized ratio; ULN: upper limit of normal

See Section 10.1.1, Adverse Events for reporting requirements related to a subject being permanently discontinued based on meeting the laboratory abnormalities list above in [Table 2](#).

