
Phlebotomy	If a subject's Hb exceeds 14.0 g/dL or the rate of rise of Hb raises concern to the Investigator, the subject may be phlebotomized based on the Investigator's clinical judgment. The method of phlebotomy will be in accordance with the investigative site's standard clinical practice.
Study Medication Stopping Rules	
Study medication must be permanently discontinued if a subject meets one of the criteria.
 
• ALT or AST >3x Upper Limit of Normal (ULN) and total bilirubin >2x ULN• ALT or AST >3x ULN and INR >1.5• ALT or AST >8x ULN• ALT or AST remains >5x ULN over 2 weeks*• ALT or AST >3x ULN with symptoms (e.g., fatigue, nausea, vomiting, right upper quadrant pain, fever, rash) or eosinophilia 
*Re-challenge generally should be avoided with ALT or AST >5x ULN unless there are no other good therapeutic options.

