Procedures – Diagnostic and therapeutic non-invasive and invasive procedures, such as surgery, should not be reported as AEs. However, the medical condition for which the procedure was performed should be reported if it meets the definition of an AE. For example, an acute appendicitis that begins during the AE reporting period should be reported as the AE and the resulting appendectomy noted under ‘Comments’.

Pre-planned therapeutic procedures not associated with a new medical condition or worsening pre-existing condition should not be reported as AEs.

Pre-existing Conditions – In this study, a pre-existing condition (ie, a disorder present before the AE reporting period started and noted on the pretreatment medical history/physical examination form) should not be reported as an AE unless the condition worsens, or episodes increase in frequency during the AE reporting period.

Abnormal Test Findings – All laboratory test results will be reviewed by the Investigator. The Investigator will utilize his/her judgment in determining if out of range laboratory values are clinically significant and will denote this using the abbreviation “CS” on the laboratory report for source documentation. Laboratory tests that are labeled as clinically significant should be reported as AEs, either separately or as part of a description of a symptomatic AE. If there are significant changes in a laboratory report from a previous visit that are determined to be clinically significant, these should also be reported as AEs. Any abnormal laboratory value which requires treatment or further diagnostic testing and/or results in discontinuation from study should be reported as an AE. An expected laboratory abnormality from a condition that is part of the medical history is not considered clinically significant for the purposes of the study unless it represents a worsening of the condition.

Abnormalities in ALT, AST and Total Bilirubin – Abnormalities in ALT, AST and total bilirubin should be reported to the Sponsor’s Medical Monitor or CRO designee within 24 hours of awareness as an SAE with ‘other medically important event’ criterion selected, if the following conditions are met:

- New elevation in ALT or AST >3 times ULN, with or without an elevation of total serum bilirubin >2 times ULN, AND

If new elevations in ALT or AST >3 times ULN, **without** an elevation of total serum bilirubin >2 times ULN are identified, the following steps are to be taken:

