- Temporary discontinuation of study medication.
- Repeat testing of ALT, AST, ALP, and total bilirubin, should be completed within 48 to 72 hours to confirm the abnormalities and to determine trend.
- Study medication should not be resumed until monitoring indicates abnormalities have resolved, are stable, or are not rapidly increasing.

Details on the management of subjects with other ALT and AST abnormalities are further described in [Section 9.4, Study Medication Stopping Rules](#).

Worsening of Anemia – In this study, it is possible that some subjects may experience a worsening of anemia. As the primary endpoint of this study assesses Hb response, worsening of anemia is captured as part of this efficacy parameter. Worsening of anemia should not be considered an AE unless the worsening of anemia is associated with a cause *other than* the subject's CKD.

Transplantation – During this long-term study, it is anticipated that some subjects may receive a kidney transplant. These events will not be recorded as AEs. Subjects will discontinue study medication for receipt of a kidney, other solid organ, hematopoietic stem cell or bone marrow transplant and should continue with the Schedule of Activities and safety assessments as described in [Section 7.5.5.2, Permanent Discontinuation of Study Medication](#).

Malignancy – During this long-term study, some subjects may develop a newly diagnosed malignancy or a recurrence of a malignancy. At the discretion of the Investigator, these subjects may continue study medication (vadadustat or darbepoetin alfa). For reporting of adverse events of malignancy, see Section 10.1.2 Serious Adverse Events.

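### Table 2 makes ALT/AST >3x ULN with INR >1.5 a mandatory permanent stop, but no INR is required after the first dose, not even at the 48 to 72 hour redraw

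*Protocol*

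**What the plan says.** All references are to the current protocol text (Version 7.0, Amendment 6).

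- **Section 9.4, Table 2.** "Study medication must be permanently discontinued if a subject meets one of the criteria in Table 2 below". There are five rows: ALT/AST >3x ULN with bilirubin >2x ULN; "ALT or AST >3x ULN and INR >1.5"; ALT/AST >8x ULN; ALT/AST staying >5x ULN over two weeks; and ALT/AST >3x ULN with symptoms or eosinophilia. A footnote discourages re-challenge above 5x ULN but leaves it open when no other good treatment exists. The synopsis repeats the rule: "Study medication must be permanently discontinued if a subject meets one of the criteria".
- **Section 10.1.1.** A new ALT/AST >3x ULN goes to the "Medical Monitor or CRO designee within 24 hours of awareness as an SAE". If the rise comes without "an elevation of total serum bilirubin >2 times ULN are identified, the following steps are to be taken", and those steps are temporary discontinuation, then "Repeat testing of ALT, AST, ALP, and total bilirubin, should be completed within 48 to 72 hours", then "Study medication should not be resumed until monitoring indicates abnormalities have resolved, are stable, or are not rapidly increasing". The next sentence refers other ALT and AST abnormalities to Section 9.4.
- **Section 9.2.2.** Coagulation tests, INR included, are drawn at Baseline. The liver panel is total bilirubin, alkaline phosphatase, ALT, AST and LDH.
- **Section 8.4.4.** The first dose follows the other Baseline procedures and may be postponed to a later visit.

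**The concern.** A stopping rule works only if the protocol obtains the measurement it depends on. The INR criterion needs an INR taken when the enzymes are raised, and a pre-dose value cannot show impaired liver synthetic function on treatment. If no INR is drawn, a subject who meets a mandatory permanent stop looks like one who meets only the temporary-hold rule. That subject may go back on drug once the enzymes are judged stable. According to the amendment history, these rules were added on regulatory guidance about potential drug-induced liver injury, so the gap falls where the amendment was meant to protect subjects.

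The second, lesser concern is that 10.1.1 does not say how its hold-and-repeat steps relate to the Table 2 rows that carry no bilirubin condition.

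**Working it through.** No sample size, power or event count enters this point. The check sets the sections side by side.

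**Where is an INR required?**

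| Place in protocol | INR required? |
|---|---|
| Baseline (9.2.2, 9.3.4, Appendix A) | Yes, before the first dose |
| Liver panel (9.2.2) | No |
| Year 1, Year 2 and Year 3/4 visit lists (9.3.5, 9.3.7, 9.3.8) | No |
| 48 to 72 hour repeat tests (10.1.1) | No: ALT, AST, ALP and total bilirubin only |
| End of Treatment laboratory list (9.3.9) | No |
| Unscheduled visits (9.3.11) | Only if the Investigator judges it medically warranted |

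Required INRs: 1 before the first dose, 0 after it. Section 9.2.2 schedules 22 on-treatment liver panels: 10 in Year 1 (Weeks 4, 8, 12, 16, 20, 24, 28, 36, 44, 52) and 4 in each of Years 2 to 4 (Weeks 64 to 208), so 10 + 3 × 4 = 22. None carries an INR. That is not itself a fault, because a routine INR is not needed. The omission that matters is at the triggered redraw.

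**Whom does the INR row reach that no other row does?** Subjects with ALT/AST above 3x but not above 8x ULN, bilirubin not above 2x ULN, no value staying above 5x for two weeks, no symptoms or eosinophilia, and INR above 1.5. For them the INR is the only thing separating a temporary hold from a permanent stop.

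**Which Table 2 rows does 10.1.1 exclude from its temporary path?**

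| Table 2 row | Excluded by the bilirubin condition? |
|---|---|
| >3x with bilirubin >2x | Yes |
| >3x with INR >1.5 | No |
| >8x | No |
| >5x over 2 weeks | No, but a subject naturally passes through hold-and-repeat before meeting it |
| >3x with symptoms or eosinophilia | No |

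One row of five is excluded and 5 − 1 = 4 are not. The amendment history explains the bilirubin exclusion by saying that this case had become a permanent stop. The same reason covers the other four rows.

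**The case against.** On the INR, three things can be said. The drug is already on hold once ALT/AST exceeds 3x ULN, so the gap affects only whether the hold becomes permanent. The group reached by the INR row alone is narrow. An Investigator who reads Table 2 is told what to check and may order an INR at an unscheduled visit. All of this is true and it limits the size of the problem. It does not remove it, because a mandatory stop still rests on an optional test. The 24-hour report brings in the Medical Monitor or CRO designee but supplies no INR.

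On the restart wording, a reader might infer that the two sections contradict each other, for example that 10.1.1 lets a subject with a stable 9x ULN and normal bilirubin restart against Section 9.4. The documents do not support that. Section 9.4 uses mandatory language and is triggered by the first 9x value. The 10.1.1 sentence says when drug should not be resumed and does not order or grant a restart. Section 9.4 sends the reader to 10.1.1 only for reporting: "See Section 10.1.1, Adverse Events for reporting requirements related to a subject being permanently discontinued". Sections 7.5.5 and 10.1.1 both point to 9.4, and 7.5.5.1 favours resumption only where it is not contraindicated. What remains is that the pointer in 10.1.1 speaks of other abnormalities, which can be read as cases outside the path just described. No sentence there says that 9.4 governs when both apply.

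**Conclusion.** The INR point stands. The permanent stop for ALT/AST >3x ULN with INR >1.5 has no required on-treatment measurement behind it: one required INR before exposure, none after, and none among the four repeat tests. A reader might go further and say that the row can never be applied, or that INR should be drawn at every liver panel. Neither follows, since discretionary testing is available and the need arises only once enzymes have risen.

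The restart wording is a matter of clarification only. Four of five rows are not expressly excluded from the temporary path, but the text already favours Section 9.4.

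This rests on reading the current version as a whole and on Baseline procedures preceding the first dose, as Section 8.4.4 states. The number of subjects affected cannot be derived from the document. No endpoint, analysis or sample size is touched. The INR addition should be made because it is cheap and bears on subject safety.

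**What to change.** 1. **Main change.** In Section 10.1.1, add INR to the 48 to 72 hour repeat tests, so that the panel reads ALT, AST, ALP, total bilirubin and INR. The cost is one extra test per triggered subject on a redraw already called for. No routine INR schedule and no change to Table 2 is needed.
2. **Clarification.** Open the temporary-interruption path in 10.1.1 with the added condition *and no Table 2 criterion is met*, and close it with *if a Table 2 criterion is met, including on repeat testing, Section 9.4 (including its footnote) applies*. The cost is two short insertions.

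An absolute sentence barring resumption should not be added to 10.1.1. It would conflict with the Table 2 footnote, which leaves narrow room for re-challenge above 5x ULN.
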